#### 6.3 SUBJECT SETS ANALYSED

Screened Set (SS): •

> The screened set consists of all subjects who signed informed consent and were screened for the trial with at least one screening procedure done at Visit 1.

• Randomised Set (RS):

The randomised set consists of all subjects who were screened for the trial and who were randomised to trial treatment, regardless of whether any trial treatment was administered.

• Treated Set (TS):

The treated set consists of all subjects who were randomised and treated with at least one dose of trial treatment. The TS is used for the analysis of safety variables.

• Full analysis set (FAS):

The full analysis set consists of all randomised subjects who were treated with at least one dose of trial treatment and had a baseline and at least one evaluable post-baseline on-treatment measurement of the primary or secondary efficacy endpoints. The FAS is used for the primary and secondary analyses of the efficacy endpoints.

• Per protocol set (PPS):

The per protocol set is nested within the FAS and only includes subjects in the FAS who do not have any important protocol deviations which are specified to be excluded from the sensitivity analysis of the efficacy endpoints using the PPS (see Table 6.2: 1). If the number of subjects in the PPS is less than 90% of the number of subjects in the FAS, then the PPS is used for the sensitivity analysis of the primary and secondary efficacy endpoints.

• Ophthalmologic Sub-study Set (EYE):

The ophthalmologic sub-study set consists of all treated subjects who consented to participate in the ophthalmologic sub-study (including late/retrospective consent to the ophthalmologic sub-study) and had evaluable ophthalmologic measurements.

## **Boehringer Ingelheim**

 TSAP for BI Trial No: 1346.9
 Page 19 of 34

 Proprietary confidential information © 2020 Boehringer Ingelheim International GmbH or one or more of its affiliated companies

#### Subject sets analysed Table 6.3: 1

	Subjects Sets Analysed					
Class of endpoints	TS	FAS		PPS		EYE
Primary endpoint – primary analysis using MCPMod & secondary analysis using pair-wise comparisons approach and descriptive statistics		X				
		X (subset)		X*		
(other) Secondary endpoints – primary analysis using MCPMod and secondary analysis using pair-wise comparisons and descriptive statistics		X		X* (only secondary efficacy endpoint)		

Safety variables	Х			Х
Variables in Ophthalmologic Sub- study				Х
Demographic/baseline variables/exposure	X		X	X

\* Only if the number of subjects in the PPS is <90% of the number of subjects in the FAS, sensitivity analysis of the primary and secondary efficacy endpoints using PPS will be conducted.

#### 6.5 **POOLING OF CENTRES**

This section is not applicable, because the study was performed in only one centre.

#### 6.6 HANDLING OF MISSING DATA AND OUTLIERS

Every effort should be taken to collect complete data at each visit for each subject. If not specified otherwise, missing data are not imputed and remain missing. Potential outliers will be reported and analysed as observed.

#### MCCB

All imputations will be carried out separately for each study visit since there may be differences in test performance at different time points.

For the domains of Working Memory (consisting Letter-Number Span test and Wechsler Memory Scale 3rd ed. Spatial Span subtest) and the Speed of Processing (consisting Trail Making Test Part A, Brief Assessment of Cognition in Schizophrenia – Symbol Coding subtest, and Category Fluency test – animal naming), if one of the tests consisting of a domain has missing value at a visit, the corresponding domain score can still be derived using the observed test raw score for that visit. If more than one of the tests consisting of a domain have missing value at a visit, the corresponding domain score is missing at that visit.

For the other five domains (Verbal Learning, Reasoning and Problem Solving, Visual Learning, Attention / Vigilance, and Social Cognition) which has only one test, if the test has missing value at a visit, the corresponding domain score is missing.

If a domain score is missing at a visit, the missing T-score of this domain can be imputed using the following algorithm:

$$\hat{T}_{ijk} = \bar{T}_{ij+} + \bar{T}_{i+k} - \bar{T}_{i++}$$

Where  $\hat{T}_{ijk}$  is the missing T-score at Visit *i* to be imputed for domain *j* of subject *k* 

 $\overline{T}_{ij+}$  is the mean T-score at Visit *i* on domain *j* from all subjects

 $\overline{T}_{i+k}$  is the mean T-score at Visit *i* on all available domains from subject *k* 

 $\overline{T}_{i++}$  is the mean T-score at Visit *i* of all available domains from all subjects.

In order to produce a more plausible imputed value that reflects the naturally occurring variability around the measure of a subject's cognitive ability, a small amount of random variance will be added to each predicted value  $\hat{T}_{ijk}$ . Multiplying the square root of the mean square error of  $\hat{T}_{ijk}$  by a random value drawn from a standard normal distribution,  $Z \sim N(0, 1)$ , the final imputed T-score of the missing domain would become:

$$\tilde{T}_{ijk} = \hat{T}_{ijk} + \sqrt{MSE(\hat{T}_{ijk}) * Z}$$

This will not only preserve the independent nature of the collected data, but also prevent exaggerating the precision of the treatment differences ( $\underline{3}$ ).

For baseline assessment, at least two-thirds of the cognitive domains (i.e., a minimum of five out of the seven domains for the MCCB overall composite score and a minimum of four out of the six domains for the MCCB neurocognitive composite score) need to be successfully assessed at baseline for it to be counted as a test occasion with non-missing baseline value.

For post-baseline assessments, at least half of the domains (i.e., a minimum of four out of the seven domains for the MCCB overall composite score and a minimum of three out of the six domains for the MCCB neurocognitive composite score) need to be successfully assessed to be considered a test occasion with non-missing value.

EOT measurement of MCCB endpoints which were collected >10 days after the last trial medication intake date will not be included in the analysis.

#### SCoRS

For the 20-item SCoRS assessment, if six or more of the 20 items have missing response, which includes the response of "N/A", for a subject at a visit, then the SCoRS total score for that subject at that visit is missing. If five or less of the 20 items have missing response, which includes the response of "N/A", for a subject at a visit, then the item with missing response will be imputed first with the average of the non-missing item values for the subject at the visit, and then SCoRS total score for the subject at the visit will be derived as the sum of the non-missing item values and the imputed item values.

Missing or incomplete AE dates are imputed according to  $(\underline{4})$ .

#### 6.7 BASELINE, TIME WINDOWS AND CALCULATED VISITS

In general, baseline values are the measurements taken on the day of the first administration of trial medication (Visit 2), and immediately prior to the first administration of trial medication. If this value is not available, the measurement at the screening visit (Visit 1) is used (PANSS and eC-SSRS), but this does not apply for MCCB measurement.

Visits are labelled according to the flow chart in the protocol: Visit 1 (screening), Visit 2 (randomisation and start of treatment, also baseline), Visit 3 (Week 3), Visit 4 (Week 6), Visit 5 (Week 9), Visit 6 (Week 12), and End of Treatment (EOT), Follow-up 1 (FU1) (7 days after EOT), Follow-up 2 (FU2) (28 days after EOT). Planned and actual test days are included in the analysis data sets and are calculated relative to the beginning of study as indicated in Table 6.7: 1 below.

Page 22 of 34

Visit	Relative to study start					
	Planned test day	Actual test day				
2	1	Day 1 – Day 2				
3	22	Day 3 – Day 39				
4	43	Day 40 – Day 60				
5	64	Day 61 – Day 81				
6 / EOT	85 for completed subjects	Day 81 – Day 101				
EOT	N/A (for early discontinued subjects)	Date of the last administration of trial medication to date of the last administration of trial medication + 8 days (for early discontinued subjects)				
FU1	EOT + 7 days	EOT + 4 days to $EOT + 10$ days				
FU2	EOT + 28 days	EOT + 21 days to EOT + 35 days				

Table 6.7: 1	Planned	and	actual	study	days
--------------	---------	-----	--------	-------	------

For efficacy endpoints with planned measurements at baseline, Week 6 and Week 12, actual measurement collected between Day 3 and Day 60 will be mapped to Week 6 and actual measurement collected between Day 61 and the actual EOT visit date will be mapped to Week 12, and baseline is the measurement collected at Visit 2. If multiple measurements are mapped into the same time point using the time window, then the first measurement will be used in the analysis.

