- ⁵ Follow-up visits are designed to capture withdrawal effects: immediate effects at 1 week after last intake of trial medication and based on half-life, again at 4 weeks after last intake of trial medication). Follow-up visit 1 may be conducted as a phone visit.
- ⁶ Informant ratings are needed for SCoRS and PANSS ratings. In person ratings are preferred whenever possible. However, if the informant is not available for in person ratings, telephone interview is acceptable. The informant must be available for a telephone interview at the visits indicated in the flowchart.
- ⁷ Study procedures of Screening Visit (Visit 1), Visit 2, Visit 4 and (e)EOT Visit can be split into 2 sequential days. If the study procedures are split into 2 sequential days, the MCCB, should be performed at the first day of the two sequential days (i.e., the day prior to Day 1), and the psychopathologic assessments (e.g. SCoRS, PANSS) should be performed on the second day.
- ⁸ Columbia Suicide Severity Rating Scale baseline/screening scale
- ⁹ Columbia Suicide Severity Rating Scale since-last-visit scale

¹³ It is recommended that the 12-lead ECG is performed 3-5 hours after intake of trial drug on visits 4 and (e)EOT.

Page 8 of 116

Proprietary confidential information © 2019 Boehringer Ingelheim International GmbH or one or more of its affiliated companies

TABLE OF CONTENTS

CLINICA	L TRIAL PROTOCOL1					
TITLE PA	TITLE PAGE1					
CLINICA	L TRIAL PROTOCOL SYNOPSIS2					
FLOW CH	IART					
TABLE O	F CONTENTS					
ABBREVI	ATIONS					
1.	INTRODUCTION16					
1.1 1.2	MEDICAL BACKGROUND					
2.	RATIONALE, OBJECTIVES, AND BENEFIT - RISK ASSESSMENT 21					
2.1 2.2 2.3	RATIONALE FOR PERFORMING THE TRIAL21TRIAL OBJECTIVES21BENEFIT - RISK ASSESSMENT22					
3.	DESCRIPTION OF DESIGN AND TRIAL POPULATION					
3.1 3.1.1 3.2	OVERALL TRIAL DESIGN AND PLAN					
2.2	CONTROL GROUP(S)					
3.3 3 3 1	SELECTION OF TRIAL POPULATION					
332	Inclusion criteria					
3.3.3	Exclusion criteria					
3.3.4	Removal of patients from therapy or assessments					
3.3.4.1	Removal of individual patients					
3.3.4.2	Discontinuation of the trial by the sponsor					
4.	TREATMENTS					
4.1	TREATMENTS TO BE ADMINISTERED					
4.1.1	Identity of BI investigational product(s) and comparator product(s)					
4.1.2	Method of assigning patients to treatment groups					
4.1.3	Selection of doses in the trial					
4.1.4	Drug assignment and administration of doses for each patient35					

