5.2 ASSESSMENT OF EFFICACY

5.2.1 Assessment of primary and secondary efficacy endpoints

Change in cognitive function, everyday living skills and disease state will be measured by the batteries, scales and questionnaires listed below.

MATRICS Consensus Cognitive Battery (MCCB) will be used to evaluate the effects of BI 425809 on cognitive functions at Screening Visit (Visit 1), Randomization Visit (Visit 2, baseline), Visit 4 and (early) End of Treatment visit (e)EOT Visit. MCCB comprises 10 tests, which assess 7 cognitive domains, including speed of processing, attention vigilance, working memory, verbal learning, visual learning, reasoning and problem solving, and social cognition. (R13-2347; R13-2373)

Schizophrenia Cognition Rating Scale (SCoRS) will be used to evaluate the everyday functional capacity at Randomization Visit (Visit 2) and (early) End of Treatment visit ((e)EOT Visit).

SCoRS is a 20-item interview-based assessment of cognitive deficits and the degree to which they affect day-to-day functions. Each item is rated on a 4-point scale. Higher ratings reflect a greater degree of impairment. The composite score will be the average of non-missing response. If five or more of the 20 items is missing, the composite score will be missing (R13-2345; R16-4322).

Page 45 of 116

Proprietary confidential information © 2019 Boehringer Ingelheim International GmbH or one or more of its affiliated companies

M.I.N.I

The Mini-international neuropsychiatric interview is a short structured clinical interview which enables researchers to make diagnoses of psychiatric disorders (R07-1303). It should be performed at Screening Visit for eligibility confirmation.

Page 46 of 116

Proprietary confidential information © 2019 Boehringer Ingelheim International GmbH or one or more of its affiliated companies

Page 47 of 116

Proprietary confidential information © 2019 Boehringer Ingelheim International GmbH or one or more of its affiliated companies

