6.2 DETAILS OF TRIAL PROCEDURES AT SELECTED VISITS

The following recommendations for the conduct of the neuropsychological assessments need to be followed:

- Each assessment of the Neuropsychological Rating Scales should preferentially be done by the same members of the site staff for a given patient throughout the study period.
- In addition, it is recommended that MCCB and SCoRS should not be administered to a patient by the same rater at the same visit to prevent bias on the SCoRS ratings.
- The MCCB should always be performed at the same time of the day, within a window of +/- 60 minutes at Visit 1, 2, 4 and/or (e) EOT. Preferably, the assessment of the MCCB is done in the morning. If the cognitive testing can't be started at the same time within the allowed time frame (±60 minutes) at a scheduled visit, the visit should be rescheduled within the allowed visit window.
- Study procedures of Screening Visit (Visit 1), Visit 2, Visit 4 and (e)EOT Visit can be split into 2 sequential days. If the study procedures are split into 2 sequential days, the MCCB,

should be performed at the first day of the two sequential days (i.e., the day prior to Day 1), and the psychopathologic assessments should be performed on the second day.

Proprietary confidential information © 2019 Boehringer Ingelheim International GmbH or one or more of its affiliated companies

- During the testing, patients are allowed to take short breaks as needed, in the judgement of the rater/investigator.
- The members of the site staff that will be administering the Neuropsychological Rating Scales have to be properly trained (either at the investigator training or individually) and training documentation has to be filed in the ISF. The training standards and standards for the conduct of the assessments will be defined for each assessment individually and can be found in the ISF. It is the responsibility of the Principal Investigator at the site to ensure proper training of all members of the site staff involved in the neuropsychological assessments.

Study procedures to be performed at each visit are listed in the Flow Chart. Additional details regarding visit procedures are provided below.

Patients do not have to come fasted for any trial visit.

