#### 5.1 PRIMARY ENDPOINT

Change from baseline in MCCB overall composite score at Week 12 is the primary efficacy endpoint. The MCCB overall composite t-score is derived from the seven domain scores obtained from a total of ten tests (see CTP Table 5.1.1: 1) and is measured at screening (Visit

1), baseline (Visit 2), Week 6 (Visit 4), and Week 12 (Visit 6). See CTP Sections 5.1.1 and 5.2.1 for details. A larger overall composite t-score indicates better cognition.

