		antipsychotics during the study		
F		Incorrect timing of endpoint measurement	ication	
	F1	Primary endpoint performed at		
		incorrect date/time		
	F1.1	MCCB measured outside the allowed time	MCCB should be performed at	None
		window	the same time of the day, i.e.	
			Within $\pm 120$ minutes at	
			visits 4 and / or EO1 as	
			administration time	
	F1 2	Baseline MCCB measured after first drug	Visit 2 MCCB should be	None
	1 1.2	administration	measured before the first drug	None
			administration	
	F1.3	EOT MCCB measured $>10$ days after last	E.g. EOT MCCB measured	None
		drug administration	>10 days after last drug	
			administration	
Ζ		Other		
	Z1	Serious issue of protocol deviation	Cases reported from site	None
			monitoring	
	Z2	Other protocol deviation affecting	E.g. substantial change in	None
		efficacy and possibly safety	nicotine consumption; positive	
			drug screening during study	
	Z3	Other protocol deviation affecting safety	E.g. abnormal hemoglobin	None
		only	measurement; not reported or	
			under-reported suicidal	
			ideation; DILI cases not	
			handled properly	

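### Does SAP 6.7 lose the baseline MCCB when Visit 2 is split and the test is done the day before Day 1?

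*SAP*

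**What the plan says.** Protocol 6.2 (and footnote 7 of the Flow Chart) gives sites a choice: "Study procedures of Screening Visit (Visit 1), Visit 2, Visit 4 and (e)EOT Visit can be split into 2 sequential days". When a site splits the visit, the MCCB "should be performed at the first day of the two sequential days (i.e., the day prior to Day 1"). The Flow Chart defines Day 1 as the day of randomization and first intake. Protocol 4.1.4 puts the first dose at the end of Visit 2.

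SAP 6.7 has three elements that bear on this:

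- A general rule, introduced as a default: "baseline values are the measurements taken on the day of the first administration of trial medication (Visit 2"), immediately before dosing. Where that value is missing, screening may stand in for PANSS and eC-SSRS, "but this does not apply for MCCB measurement".
- Table 6.7: 1, which gives Visit 2 the actual test days Day 1 to Day 2 and starts Visit 3 on Day 3.
- A rule limited to efficacy endpoints planned at baseline, Week 6 and Week 12. It sets its own day windows and says that "baseline is the measurement collected at Visit 2".

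Elsewhere baseline is also defined by visit. SAP 5.1 lists the MCCB time points after screening as "baseline (Visit 2), Week 6 (Visit 4), and Week 12 (Visit 6"), and Protocol 5.2.1 has "Randomization Visit (Visit 2, baseline"). In SAP Table 6.2: 1, deviation F1.2 concerns a baseline MCCB taken after the first dose. Its comment begins "Visit 2 MCCB should be" and goes on to require a test before dosing, with no same-day condition.

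**The concern.** A test on the day before Day 1 is exactly what the protocol prescribes for a split Visit 2. It is not on the day of first dosing, it lies before the Day 1 to Day 2 window, and the screening value may not replace it. No sentence in SAP 6.7 mentions the split visit or says which baseline rule takes precedence.

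Baseline MCCB enters the primary analysis twice: in the change score, and as a covariate in the repeated-measures model (SAP 7.4.1). If a programmer applied the day-of-dosing rule literally, a split-visit patient would have no usable baseline MCCB. SCoRS is done on the second day, so the patient could still qualify for the full analysis set through SCoRS and yet contribute nothing to the primary model. Loss of protocol-compliant patients from the primary analysis through a date rule would be a real defect.

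**Working it through.** **1. A Day −1 MCCB against each rule**

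Days are counted from first intake, as in the protocol.

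| Rule | Test applied | Day −1 MCCB accepted? |
|---|---|---|
| SAP 6.7 general rule | same day as first dose | no |
| Table 6.7: 1, Visit 2 row | Day 1 to Day 2 | no |
| SAP 6.7 Week 6 mapping | Day 3 to Day 60 | no (and not wanted) |
| SAP 6.7 efficacy rule | collected at Visit 2 | yes |
| SAP 5.1, Protocol 5.2.1 | Visit 2 | yes |
| F1.2 | before first dose | yes, not a deviation |

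**2. Which rule applies to the MCCB**

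- The general rule is worded as a default. The efficacy rule is limited to endpoints with the baseline, Week 6 and Week 12 schedule, and SAP 5.1 gives the MCCB that schedule. A specific rule displaces a default.
- Within its scope the efficacy rule visibly replaces the table. Table 6.7: 1 separates Day 3 to 39 (Visit 3) from Day 40 to 60 (Visit 4), whereas the efficacy rule sends all of Day 3 to 60 to Week 6. The table's day ranges therefore do not drive MCCB mapping after baseline, and nothing suggests that they should at baseline.
- SAP 6.7 labels visits by the protocol flow chart. Footnote 7 of that chart treats both days of a split as one visit, so an MCCB on the first day is a Visit 2 MCCB.
- Protocol 6.2.2 delays the IRT call until the neuropsychological endpoints are done. A preceding-day MCCB is therefore pre-dose, which is the property a baseline needs.

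**3. What the literal reading would cost, for scale only**

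Protocol 7.7 states 80% average power with 75 evaluable patients per active arm and 150 on placebo (450 in total), effect size 0.35 and one-sided alpha 0.05.

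The six shapes can be recovered from SAP Table 7.4.1: 1. Divide each contrast by the arm weight (2:1:1:1:1), shift placebo to zero, and scale the maximum to 0.35. Check on the linear row: −0.593/2 = −0.2965, and the range is 0.762 + 0.2965 = 1.0585. The 2 mg point is (−0.212 + 0.2965)/1.0585 = 0.080 = 2/25, as it should be.

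For contrast c and arm sizes n, with SD 1, the noncentrality is Σcμ / √(Σc²/n). Power is the chance that the largest of the six t statistics exceeds the critical value. With 400,000 simulations the critical value is 2.07. Power by shape runs from 75.4% to 85.7%, and the average is 81.7%, close to the stated 80%.

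| Assumed share lost | Evaluable | Average power | Change |
|---|---|---|---|
| 0% | 450 | 81.7% | – |
| 5% | 450 × 0.95 = 427.5 | 80.0% | −1.7 points |
| 10% | 450 × 0.90 = 405 | 77.8% | −3.9 points |

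The shares are assumptions, since the documents give no frequency of split visits. Under the efficacy rule the share lost is 0%.

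**The case for a change.** The strongest reply is that the efficacy rule depends on what counts as Visit 2, and the same section windows Visit 2 as Day 1 to Day 2. SAP Table 5: 1 also heads the baseline column Day 1, and SAP Table 6.1: 2 runs the screening period up to first dosing. A date-driven program might therefore label a Day −1 test as screening. Version 4 of the SAP revised 6.7 to clarify its windows and still did not mention the split.

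It is true that no sentence states precedence and that the Visit 2 row does not name the preceding day. The inference that the test is lost does not follow:

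- The periods in Table 6.1: 2 are analysis periods. Every proper baseline precedes first dosing, so those labels cannot be what decides baseline.
- Table 6.7: 1 counts days from the beginning of the study, which 6.7 leaves undefined. Counted from the first day of a split Visit 2, Day 1 to Day 2 would cover both days. That sits badly with the protocol's Day 1, so it is not decisive, but the table is not clear evidence for exclusion.
- SAP section 3 assumes familiarity with the protocol, and SAP 6.2 has deviations reviewed blinded before unblinding. A patient with a compliant Visit 2 MCCB but no derived baseline would be an obvious anomaly.

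A related worry is that when several MCCBs map to one time point, SAP 6.7 uses the first, so an early test could displace the Day 85 value. MCCB is planned only at Visits 1, 2, 4 and (e)EOT, and Protocol 6.2.2 bars an EOT cognitive test before Day 85. The latest on-time Visit 4 is Day 43 + 3 = 46, which is 61 − 46 = 15 days short of the Week 12 window. No on-schedule completer is affected.

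Choosing the test closest to the planned day would not clearly be better. Take Visit 4 and last dose on Day 40, with an early EOT test on Day 45. The distances from Day 43 are 3 and 2, so the closest-day rule discards the on-treatment value for one taken five days after the last dose. Tests on Days 41 and 45 would tie. The existing rule is pre-specified and deterministic.

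**Conclusion.** No change to the plan is needed. The general baseline rule and the Visit 2 row do not mention the preceding-day MCCB of a split visit. The endpoint-specific rule, flow-chart visit labelling and F1.2 together take that test as baseline. On this reading the number of patients lost is zero, and the 450 evaluable patients behind the power statement are untouched. The power reductions in the working are not an estimate of harm, because they need both the literal reading and an undocumented share of split visits.

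The conclusion assumes that a split-visit MCCB is recorded under Visit 2, as the flow chart directs, and that the specific rule is taken to govern over the default. A clarifying line would do no harm, but the result does not depend on it. The first-measurement rule affects no on-schedule completer, and replacing it shows no gain. F1.2 already lists a post-dose baseline as a deviation and excludes nobody for it, so nothing needs adding there.

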5. VARIABLES AND THEIR ASSESSMENT

5.1 TRIAL ENDPOINTS

5.1.1 **Primary Endpoint(s)**

Change from baseline in cognitive function as measured by the composite MCCB score after 12 weeks of treatment is the primary efficacy endpoint.

The 10 tests of the MCCB with corresponding cognitive domains are listed in Table 5.1.1: 1 below:

Test	Domain
Trail Making Test, Part A (TMT)	Speed of Processing
Brief Assessment of Cognition in Schizophrenia, symbol coding subtest (BACS SC)	Speed of Processing
Hopkins Verbal Learning Test – Revised (HVLT-R), immediate recall	Verbal Learning
Wechsler Memory Scale, 3 rd ed. Spatial span subtest (WMS-III SS)	Working Memory (nonverbal)
Letter-Number Span test (LNS)	Working Memory (verbal)
Neuropsychological Assessment Battery, mazes subtest (NAB mazes)	Reasoning and Problem Solving
Brief Visuospatial Memory Test- Revised (BVMT-R)	Visual Learning
Category Fluency test, animal naming	Speed of Processing
Mayer-Salovey-Caruso Emotional Intelligence Test, managing emotions branch (MSCEIT TM ME)	Social Cognition
Continous Performance Test, Identical Pairs version (CPT-IP)	Attention/ Vigilance

Table 5.1.1: 1 MCCB tests and cognitive domains (R13-2373)

Proprietary confidential information © 2019 Boehringer Ingelheim International GmbH or one or more of its affiliated companies

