Proprietary confidential information © 2019 Boehringer Ingelheim International GmbH or one or more of its affiliated companies

End of Treatment (Visit 6):

Study procedures have to be completed according to the Flow Chart.

Cognitive assessments of EOT Visit cannot be performed before Day 85. The final evaluation of cognitive function must be performed after patients complete 12-week treatment period. For the patients who discontinue the study medication early, the cognitive assessments of (e)EOT Visit must be performed within 7 days after last dose intake.

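### SAP 6.7 opens the Week 12 efficacy window at Day 61 and keeps the first value in it, so some early end-of-treatment MCCB tests are analysed as 12-week values

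*SAP*

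**What the plan says.** **Endpoint.** Protocol 5.1.1: "Change from baseline in cognitive function as measured by the composite MCCB score after 12 weeks of treatment is the primary efficacy endpoint". SAP 5.1: "Change from baseline in MCCB overall composite score at Week 12 is the primary efficacy endpoint".

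**Schedule.** Protocol 5.2.1 places the MCCB at screening and then at "Randomization Visit (Visit 2, baseline), Visit 4 and (early) End of Treatment visit (e)EOT Visit". Visit 5 (Week 9) has none.

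**Timing of the last test.** Protocol 6.2.2 says "Cognitive assessments of EOT Visit cannot be performed before Day 85" and "The final evaluation of cognitive function must be performed after patients complete 12-week treatment period". For patients who stop early, the same paragraph says "the cognitive assessments of (e)EOT Visit must be performed within 7 days after last dose intake".

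**Windows in SAP Table 6.7: 1.** Visit 5 covers Days 61 to 81. Visit 6/EOT, planned for Day 85, covers Days 81 to 101, so the two rows share Day 81. A separate row places the EOT of early discontinuers between the last dose and 8 days after it.

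**Efficacy mapping in the text below that table.** Days 3 to 60 go to Week 6. For later tests, "actual measurement collected between Day 61 and the actual EOT visit date will be mapped to Week 12". If several values map to one time point, "then the first measurement will be used in the analysis".

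**Other limits.** SAP 6.6 drops an EOT MCCB taken more than 10 days after the last dose but sets no earliest study day. Protocol 7.5 does not impute completely missing visits and leaves them to the MMRM under missing at random.

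**The concern.** The estimate is labelled as the effect after 12 weeks, but the window that feeds it reaches back to a test made 60 days after the first dose. The Week 12 mean can therefore mix full-course values with values from patients who had less treatment and had already stopped.

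The cut is also abrupt. Take a patient tested on schedule at Day 43 who then stops. An early end-of-treatment test on Day 60 maps to Week 6 and is discarded, because the Day 43 value came first. The same test on Day 61 becomes the patient's primary endpoint value.

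The first-value rule raises a second, rarer problem. If a patient has two MCCBs in the Week 12 window, one before Day 85 and one at Day 85, the rule analyses the earlier one, although only the later one matches the endpoint definition. The visible MCCB timing codes in SAP Table 6.2: 1 (F1.1 to F1.3) concern time of day, a baseline taken after dosing, and tests more than 10 days off drug. None names an EOT test before Day 85, and none excludes anyone.

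**Working it through.** **1. The plan's own figures.** Protocol 7.7 needs 75 evaluable patients per active arm and 150 on placebo, and assumes 10% dropout. 75/0.9 = 83.3, rounded up to 84; 2 × 84 = 168; 4 × 84 + 168 = 504. This matches. A simulation of the MCPMod maximum-contrast test (400,000 draws, the six contrasts of SAP Table 7.4.1: 1, effect size 0.35, one-sided alpha 0.05, adjusted critical value 2.07) gives 81.9% average power at 450 evaluable, and 75.8% to 85.8% by model. The protocol states an average of 80%.

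**2. Window arithmetic.**
- Day 61 is 60 days after the first dose: 60/7 = 8.6 weeks. Day 85 is 84/7 = 12.0 weeks.
- Gap to the planned day: 85 − 61 = 24 days. Gap to the table's Visit 6 window: 81 − 61 = 20 days.
- Midpoint of the two planned test days: (43 + 85)/2 = Day 64. Days 61 to 63 are nearer to Week 6 than to Week 12.

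**3. How many patients.** Assumptions: 10% dropout, stopping spread evenly over 84 days, an early EOT MCCB from every dropout.
- Dropouts: 504 × 0.10 = 50.4.
- Tested on Days 61 to 84: 50.4 × 24/84 = 14.4, or 14.4/504 = 2.9% of those randomised.
- As a share of Week 12 values: 14.4/(453.6 + 14.4) = 3.1%.
- Of the 14.4, Days 61 to 63 hold 50.4 × 3/84 = 1.8, Days 64 to 80 hold 50.4 × 17/84 = 10.2, and Days 81 to 84 hold 50.4 × 4/84 = 2.4.

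**4. What this could do to power.** Let f be the share of Week 12 values taken on Days 61 to 84, and r the drug effect in those values relative to the Week 12 effect. The documents give neither. With effect = 0.35 × (1 − f(1 − r)) and 450 values held fixed:

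| f | r = 0.5 | r = 0 |
|---|---|---|
| 2% | 81.2% | 80.4% |
| 5% | 80.1% | 78.2% |
| 10% | 78.1% | 74.1% |

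The 3.1% from step 3 lies between the first two rows. The 10% row would need every planned dropout to fall in these 24 days.

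**5. Routes to two tests in one window.** The schedule produces none. A Visit 4 test on Day 61 would be 18 days late against a ±3-day window, and the Visit 2 kit lasts 42 + 7 = 49 days (Protocol 4.1.4). What remains is a premature EOT test that is later repeated, or an unscheduled test.

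**The case against.** The strongest defence is that the mapping uses the last on-treatment observation of late discontinuers, which is a legitimate choice. Protocol 6.2.2 requires these tests within 7 days of the last dose, and the SAP's on-treatment period runs through an 11-day residual effect period. Setting them to missing would lean harder on missing at random. This stands: removing all such values from the primary analysis would be a trade-off, not a correction.

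The other side is also right on five readings that a reader might infer but the documents do not support:
- *A Day 61 to 84 test breaches the Day 85 bar.* For an early stopper it complies with 6.2.2. It conflicts only with the 12-week label.
- *A 9-week test displaces a 12-week one.* No MCCB is scheduled at Week 9, and an early stopper has no later value to lose. Displacement needs a duplicate.
- *Keeping the first value always prefers the one furthest from target.* This is untrue for two tests on or after Day 85, where the first is the closest.
- *The rule biases against the drug.* Neither the effect at the early tests nor its direction relative to Week 12 is given.
- *No sensitivity analysis covers this.* SAP Table 6.3: 1 has an unlabelled row using a subset of the FAS, and the visible text passes from 7.4.1 to 7.5. Blacked-out text may contain one.

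On repeats, the plan provides for none, and a second MCCB a few days later may carry a practice effect, so keeping the first can be argued. But the SAP does not argue it. Its history table says only that the windows were clarified after meetings, with no reason for Day 61 or for the first value.

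**Conclusion.** The point holds as a minor one. The SAP's efficacy mapping disagrees with its own visit table and lets values from well before Day 85 count as Week 12.

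Under even stopping, about 14 of 504 patients are affected. That is an upper figure on that assumption, because early EOT procedures depend on the patient's agreement (Protocol 3.3.4.1). Stopping concentrated in Days 61 to 84 would raise it.

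The effect on the arm means is probably small. At about 3% of Week 12 values and half the effect, average power stays above the planned 80%; even with no effect in those values it stays between 78.2% and 80.4%. These figures rest on the assumed f and r and are not an estimate of bias.

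The duplicate case should be uncommon. It still matters for any patient concerned, because the rule as written would then replace a Day 85 value with an earlier one.

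**What to change.** In SAP 6.7, for the MCCB:

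1. If several values map to one time point, use the one closest to the planned day (Day 43 or Day 85). For completers, prefer a test on or after Day 85. The preference is needed because the table's Visit 6 window itself opens 4 days before the protocol's earliest day.
2. Align the Week 12 efficacy window with Table 6.7: 1, remove the shared Day 81, and assign early EOT values to the nearest planned day, with a stated tie rule for Day 64. This moves only about 2 of the 14 patients; most of the rest stay at Week 12 in the primary analysis, which is why item 3 is needed.
3. Unless a blacked-out section already does so, add one sensitivity analysis that sets early EOT values before Day 81 to missing at Week 12 and leaves them to the MMRM. Relative to the current mapping this affects about 12 patients (1.8 + 10.2).
4. Reconcile the three limits on the early EOT test after the last dose: 7 days in Protocol 6.2.2, 8 days in SAP Table 6.7: 1 and 10 days in SAP 6.6.

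The cost is SAP wording and one extra run, with slightly fewer Week 12 values in that run. No added patients are needed: 504 × 0.9 = 453.6 covers the 450 evaluable.
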